7.9.1.2.5 Determination of Subjects' Data for Analysis

The return to work analysis will consist of patients in the ITT population who report having an occupation (employed or independent worker, including stay-at-home parent) at their baseline visit. The anatomic closure analysis will consist of the ITT population with available data will be used for the primary analysis on key secondary endpoints. For a sensitivity analysis, AT and PP populations will be used on key secondary endpoints.

7.9.1.3 Secondary Endpoints

Data supporting the following endpoints will be collected for both the CEAP 2-5 Randomized Studies. When appropriate, data will be evaluated for the CEAP 2-5 Randomized Studies to compare the VenaSeal™ system to surgical stripping or ETA. Data may also be pooled for all VenaSeal™ system subjects from the CEAP 2-5 randomized studies and VLU study as appropriate.

Data from VenaSeal vs. Surgical Stripping Study will be collected through the 12-month visit.

The secondary endpoints will provide additional clinical evidence related to effectiveness, safety, and patient and provider experience. The p-values from any pre-specified hypothesis tests of the remaining secondary objectives will not be adjusted for multiple comparisons. Reports or publications that contain these p-values will state that an appropriate multiple comparisons adjustment was not performed.

Descriptive statistics for the secondary endpoints will be provided. For categorical variables, the count and percentage of subjects with each outcome will be presented. For continuous variables, summary statistics (mean, standard deviation, median) will be presented. More analysis methodology details are provided below.

7.9.1.4 Effectiveness secondary endpoints

1. Anatomic closure of the primary target vein at 30 days, and 12, 24, 36, 48 and 60 months

Hypothesis

There is no formal hypothesis test for this study objective.

Endpoint Definition

- For subjects treated with the VenaSeal™ system or ETA it is defined as DUS showing vein closure along the entire treated vein segment with no discrete segments of patency exceeding 5 cm.
- For subjects treated with surgical stripping, anatomic closure of the target vein is defined as absence of clinically significant remnant refluxing truncal vein incompetency and no discrete segments of patency exceeding 5 cm at 30 days and 12 months only.

Lack of anatomic closure on the date of the index procedure will not be considered for this endpoint, since some treatments may not achieve closure immediately.

Analysis Methods

The probability of (primary) target vein closure of any primary target vein at each time point will be summarized by treatment arm in each study. The probability for each treatment arm will be estimated using the Kaplan-Meier method. Day zero is the date of the index procedure. The censoring time is the time to last study visit (scheduled or unscheduled), the time point for analysis, or time to exit, whichever comes first.

Determination of Subjects for Analysis

The anatomic closure analysis will consist of the ITT population.

2. Anatomic closure of target vein at 30 days, and 6, 12, 24, 36, 48 and 60 months

Hypothesis

There is no formal hypothesis test for this study objective.

Endpoint Definition

- For subjects treated with the VenaSeal™ system or ETA, anatomic closure of the target vein is defined as DUS showing target vein closure along the entire treated vein segment with no discrete segments of patency exceeding 5 cm.
- For subjects treated with surgical stripping, anatomic closure of the target vein is defined as the absence of clinically significant remnant refluxing truncal vein incompetency and no discrete segments of patency exceeding 5 cm at 30 days, 6 and 12 months only.

Lack of anatomic closure on the date of the index procedure will not be considered for this endpoint, since some treatments may not achieve closure immediately.

Analysis Methods

The probability of target vein closures of any target vein at each time point will be summarized by treatment arm in each study. The probability for each treatment arm will be estimated using the Kaplan-Meier method. Day zero is the date of the index procedure. The censoring time is the time to last study visit (scheduled or unscheduled), the time point for analysis, or time to exit, whichever comes first.

Determination of Subjects for Analysis

The anatomic closure analysis will consist of the ITT population.

3. Technical success of each target vein immediately post-index procedure

Hypothesis

The following hypothesis will be tested:

$$H_0: \pi_A = \pi_C$$

$$H_a: \pi_A \neq \pi_C$$

Where π_A and π_C are the percentage of technical success post-index procedure in the VenaSeal™ system arm and the ETA or surgical stripping arm, respectively.

Endpoint Definition

- For subjects treated with VenaSeal™ system or ETA this is defined as DUS showing vein closure along the entire treated vein segment with no discrete segments of patency exceeding 5 cm.
- For subjects treated with surgical stripping this is defined as the absence of clinically significant remnant refluxing truncal vein incompetency and no discrete segments of patency exceeding 5 cm.

Analysis Methods

The percentage of technical successes will be summarized by treatment arm in each study. The numerator is the number of technical successes, the denominator is the number of target veins treated at the index procedure. Fisher's Exact test will be used to compare arms for the endpoint.

Determination of Subjects for Analysis

The technical success analysis will consist of the AT population.

4. Reintervention of any target vein (including primary target vein) through 60 months, assessed at each follow-up visit. Subjects enrolled in the VenaSeal vs. Surgical Stripping Study will be followed through the 12 months visit only.

Hypothesis

The following hypothesis will be tested:

$H_0: r_A = r_C$

$H_a: r_A \neq r_C$

Where r_A and r_C are the rates of reintervention in the VenaSeal™ system arm and the ETA or surgical stripping arm, respectively.

Endpoint Definition

A reintervention is a retreatment of any segment of any target vein in the target limb previously treated as part of the study at the index procedure.

Analysis Methods

The rate of reintervention will be summarized by treatment arm in each study. The rate is calculated such that the numerator is the number of reinterventions and the denominator is the number of vein-years of follow-up. The amount of follow-up per person is defined as their date of exit or last known follow-up minus their date of index procedure. The vein-years is the amount of person-years times the number of target veins. A Poisson model will compare the rate of reintervention between treatment arms, using the number of reinterventions as the outcome and the person years of follow-up as an offset.

Determination of Subjects for Analysis

The reintervention analysis will consist of the ITT population.

5. Time to reintervention of any target vein (including primary target vein) through 60 months, as measured by the time between the index procedure and the first reintervention procedure. Subjects enrolled in the VenaSeal vs. Surgical Stripping Study will be followed through the 12 months visit only.

Hypothesis

The following hypothesis will be tested:

$H_0: S_A(t) = S_C(t)$

$H_a: S_A(t) \neq S_C(t)$

where $S_A(t)$ and $S_C(t)$ are the survival function estimates at time point t in the VenaSeal™ system arm and the ETA or surgical stripping arm, respectively. In the VenaSeal vs. Surgical Stripping Study, $t=12$ months and is otherwise $t=60$ months.

Endpoint Definition

A reintervention is a retreatment of any segment of any target vein in the target limb previously treated as part of the study at the index procedure.

Analysis Methods

The time to reintervention will be summarized by treatment arm in each study. Time to the first reintervention of any target vein by treatment will be presented with Kaplan-Meier estimation. Day zero is the date of the index procedure. The censoring time is the time to study exit, the later of either the last

contact date or the discontinuation date, or the time point for analysis, whichever comes first. A log-rank test will be used to compare arms.

Determination of Subjects for Analysis

The reintervention analysis will consist of the ITT population.

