4. EQ-5D-5L
5. AVVQ
6. SF-36
7. Patient reported outcomes:
 - a. Pain score measured by using NRS scale of 0-10
 - b. Ability to return to work/normal activities (only if not returned to work/normal activities by 7-day visit)
 - c. VenousDQoL
 - d. Patient-reported symptoms
8. AE assessment
9. Healthcare utilization since last study visit
10. VLU Study:
 - a. Active ulcers: ulcer assessment, ongoing wound care, photographs for core laboratory, healing status
 - b. Post-healing confirmation: recurrence status.

If COVID-19 prevents patients from returning for follow-up visits at 7 or 30 days (due to subject contracting COVID-19 or due to site policy), these visits may be conducted through telehealth or other alternative methods to be discussed with the Medtronic study team prior to execution.

3+ Months (calculated as 90 days): Optional for all subjects

1. Adjunctive therapy: Number of phlebectomy sites and/or sclerotherapy injections administered (data collected through 60 months).
2. AE Assessment.

6 months (+/- 4 weeks), 12, 24, 36(+/-8 weeks)

Subjects will return to the site for follow-up to conduct the following assessments (limb-specific assessments are of the target limb only). VenaSeal vs Surgical Stripping Study subjects will be followed up to and including 12 months:

1. DUS:
 - a. Areas of patency, if any
 - b. Reflux along treatment area
 - c. Evidence of thrombus
2. CEAP classification
3. rVCSS
4. Venous Treatment Satisfaction Questionnaire (VenousTSQs) (up to 12 months visit)

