5. EQ-5D-5L
6. AVVQ
7. SF-36 (up to 12-month visit)
8. Patient reported outcomes:
 - a. VenousDQoL
 - b. Patient-reported symptoms (up to 12-month visit)
9. Adjunctive therapy assessment
10. AE assessment
11. Healthcare utilization since last study visit
12. VLU Study:
 - a. Active ulcers: ulcer assessment, ongoing wound care, photographs for core laboratory, healing status
 - b. Post-healing confirmation: recurrence status.

48, 60 months (+/-8 weeks)

Subjects will return to the site for follow-up to conduct the following assessments (limb-specific assessments are of the target limb only). Subjects may also complete 48 and 60 months visit remotely per physician's discretion if subjects cannot return to the site for follow-up.

1. DUS:
 - a. Areas of patency, if any
 - b. Reflux along treatment area
 - c. Evidence of thrombus
2. CEAP classification
3. rVCSS

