4. EQ-5D-5L
5. AVVQ
6. Patient reported outcomes:
 - a. VenousDQoL
7. Adjunctive therapy assessment
8. AE assessment
9. Healthcare utilization since last study visit
10. VLU Study:
 - a. Active ulcers: ulcer assessment, ongoing wound care, healing status
 - b. Post-healing confirmation: recurrence status.

If remote visit occurs, the following assessments can be completed via telehealth and/or hard-copy of questionnaires required to be completed via mail. Questionnaires can be sent to subjects via mail and subjects can complete and return it back to the site via mail.

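### Long-term closure is censored at the last study visit, not the last duplex scan, so remote 48- and 60-month visits add unscanned event-free time and can only raise the closure estimate or leave it unchanged

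*SAP*

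**What the plan says.** SAP 7.9.1.4, item 1, covers closure of the primary target vein. For VenaSeal and ETA subjects closure is "defined as DUS showing vein closure along the entire treated vein segment with no discrete segments of patency exceeding 5 cm". "The probability for each treatment arm will be estimated using the Kaplan-Meier method". The follow-up rule is: "The censoring time is the time to last study visit (scheduled or unscheduled), the time point for analysis, or time to exit", taking the earliest. Item 2 (closure of target veins) and SAP 7.9.2.3, items 4 and 5 (VLU Study), use the same rule. So does SAP 7.9.1.2.4 for the 6-month key secondary test. Items 1 and 2 of 7.9.1.4 both state: "There is no formal hypothesis test for this study objective". SAP 7.9.2.2 says likewise for the VLU secondary endpoints.

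Protocol section 10.10, under the 48- and 60-month visits: "Subjects may also complete 48 and 60 months visit remotely per physician's discretion if subjects cannot return to the site for follow-up". It continues: "If remote visit occurs, the following assessments can be completed via telehealth and/or hard-copy of questionnaires". The list that follows contains EQ-5D-5L, AVVQ, VenousDQoL, adverse events, healthcare utilization and ulcer items. It contains no DUS. Section 10.11 requires only an adverse-event assessment at an unscheduled visit and leaves DUS to the physician. For COVID-19 disruption at day 7 or day 30, section 10.10 says "these visits may be conducted through telehealth or other alternative methods".

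**The concern.** Re-opening can be detected only on a scan, but follow-up for the endpoint runs to the last visit of any kind. Take a subject scanned closed at 36 months who then completes the 48- and 60-month visits by telephone and post. Under the SAP rule this subject counts as at risk and event-free until 60 months. A silent re-opening in that period has no way to enter the data, yet the subject enlarges the denominator for every event seen in others.

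No other SAP text closes the gap. Section 7.4 deals with drop-outs, and the available-data restriction in 7.9.1.2.5 belongs to the key secondary analysis. The SAP does tailor censoring by endpoint: time to reintervention (7.9.1.4, item 5) runs to last contact or discontinuation, which suits an event that can be learned by telephone. Closure needs a rule tied to the scan. At stake is the five-year durability estimate, the long-term result most likely to be quoted by arm.

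**Working it through.** **No stated figure to reproduce.** The documents give no expected value, sample size or power for closure at 48 or 60 months. The nearest closure figure is the 6-month non-inferiority calculation (95% vs. 95.4%, margin 10%, one-sided 0.0167, 80% power). With Farrington-Manning variance it gives 118.3, so 119 per arm as stated, with power 80.3%.

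**Inputs** (protocol section 4.1 unless noted)
- No late failures: the five-year extension reports none between 36 and 60 months. h = 0, S(36) = 94.4%.
- eSCOPE: 91.4% at 6 months, 88.5% at 36 months, 2.5 years apart. h = 1 − (0.885/0.914)^(1/2.5) = 1.28% per year.
- VeClose, VenaSeal arm: 99.0% at 3 months, 94.4% at 36 months, 2.75 years apart. h = 1 − (0.944/0.990)^(1/2.75) = 1.72% per year.
- Share f of subjects remote at both 48 and 60 months with no later scan: not given. Assumed 10%, 25% and 50%.

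**Formulas.** Under the SAP rule a fraction f of the risk set cannot produce an event, so each yearly Kaplan-Meier drop is h(1 − f) rather than h.
- Censoring at last DUS: S(60) = S(36) × (1 − h)²
- SAP rule: S(60) = S(36) × [1 − h(1 − f)]²

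Example (VeClose rate, f = 50%): 0.944 × (1 − 0.0172)² = 91.2% against 0.944 × (1 − 0.0086)² = 92.8%, a gap of 1.6 points.

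| Re-opening after 36 months | Last-DUS rule, 60 months | SAP rule, f = 10% | f = 25% | f = 50% |
|---|---|---|---|---|
| None | 94.4% | 94.4% (0) | 94.4% (0) | 94.4% (0) |
| 1.28% per year | 86.2% | 86.5% (+0.2) | 86.8% (+0.6) | 87.4% (+1.1) |
| 1.72% per year | 91.2% | 91.5% (+0.3) | 92.0% (+0.8) | 92.8% (+1.6) |

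Gaps were taken before rounding. At 48 months they are about half as large, for example 92.8% against 93.6% (+0.8) in the last cell.

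**Simulation check.** Set-up: 132 per arm (264/2), constant re-opening of 1.71% per year from day 0, remote status independent of re-opening, visits on target days, curve read at day 1825.
- f = 25%: SAP rule 92.5%, last-DUS rule 91.7%, truth 91.7%.
- f = 50%: SAP rule 93.5%, last-DUS rule 92.0%, truth 91.9%.

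The SAP-rule estimate was at or above the last-DUS estimate in every simulated trial. That must be so, because added event-free time cannot lower a Kaplan-Meier factor.

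**Sensitivity to visit timing.** With visits spread over their full windows and f = 50%, the gap was 1.9 points (93.9% vs. 92.0%). Reading the curve at the end of the window (day 1881) pulled both estimates well below the truth: at f = 25%, 86.4% and 84.2% against 91.8%. The risk set empties as subjects reach their final visit. The ordering of the two rules did not change. The sizes above describe the effect of the censoring rule with visits near target.

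**The case against.** The other side has real points.

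- **Descriptive endpoint.** No test, alpha or success claim depends on 48- or 60-month closure. This stands and limits the severity.
- **The bias may be zero.** The extension's report of no failures after 36 months gives no overstatement at all. This stands as the lower end of the range. It is limited reassurance, since 89 of the 242 treated subjects attended that 60-month visit, under a separate protocol.
- **DUS is still scheduled.** Protocol 10.5 and Table 6 keep DUS at 48 and 60 months and allow it on another day within the window. But the remote option is for subjects who cannot return to the site, and section 10.1 says other clinics should not be used instead. Where a scan is done, a last-DUS rule credits it.
- **Some subjects are unaffected.** Someone remote at 48 months but scanned at 60 is handled alike under both rules.
- **Last-DUS censoring is not free of bias.** It assumes that a remote visit is unrelated to re-opening. In an extreme assumed case, true closure falls from 94.4% to 90%, every re-opened subject is scanned, and 40% of still-closed subjects are remote. The scanned group is then 4.4 + 0.6 × 90 = 58.4, and the last-DUS estimate is 94.4 × (1 − 4.4/58.4) = 87.3%, while the SAP rule gives 90.0%. This stands, and calls for a sensitivity analysis. It does not justify counting unscanned time as observed.

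A reader might also infer more than the documents support:
- *Remote visits will be heavily used, because only 89 of 242 returned in the extension.* That figure shows attrition. Subjects with no visit stop contributing under either rule.
- *The overstatement is 3 or 4 points.* For example, a true fall from 94.4% to 88% over the two years implies 1 − √(0.88/0.944) = 3.5% per year, above every rate in the protocol's background.
- *The 6-month non-inferiority test is compromised.* It shares the sentence, but no remote visit is planned at 6 months. It is exposed only through visits where no DUS was done. Day-7 or day-30 telehealth changes nothing for anyone scanned later.
- *The comparison between arms is distorted.* That would require remote use or re-opening to differ by arm. The documents give no figure for either, and no test is planned.

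**Conclusion.** The concern holds in a limited form and merits a should-fix. As written, the rule treats unscanned time as event-free follow-up. Its effect on 48- and 60-month closure in the VenaSeal vs. ETA and VLU studies is upward or nil, and the enlarged risk set makes the intervals too narrow. With 10% to 50% of subjects remote at both late visits (assumed) and re-opening of 0 to about 1.7% per year (from the protocol's background), the overstatement at 60 months is 0 to about 1.6 points with visits on target days. It is zero if nothing re-opens after 36 months. These sizes assume that remote attendance is unrelated to re-opening. The Surgical Stripping Study ends at 12 months and has no 48- or 60-month exposure. It would be too strong to say that a remote visit counts as proof of closure, or that long-term closure is certainly overstated. The subject is simply kept in the risk set without an event.

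**What to change.** In SAP 7.9.1.4 (items 1 and 2) and 7.9.2.3 (items 4 and 5), replace the last-visit clause of the censoring rule with *date of the last DUS that assessed the (primary) target vein*. Make the same change in 7.9.1.2.4 for consistency. State that a visit without DUS, whether remote or unscheduled, does not extend closure follow-up. Use the scan date rather than the visit date, since the protocol lets them differ within a window.

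Report the number scanned at each time point, by arm, beside each estimate. Add a sensitivity analysis, for example an interval-censored estimate or the present rule shown alongside, because last-DUS censoring assumes remote attendance is unrelated to re-opening.

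The cost is a SAP wording change, one extra analysis, and dates that are already collected. The long-term estimates become slightly less favourable and their intervals wider. The change should be made before the 48-month data are analysed.

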9.3. Target Veins and Target Limb

Multiple refluxing superficial truncal veins (e.g., GSV, SSV, accessory saphenous veins) in the same target limb that are each at least 10 cm in length may be enrolled and treated in the study. During screening and prior to randomization, sites will identify at least one incompetent target vein. The primary target vein should be the saphenous vein which at the investigator's discretion is most likely responsible for the greatest portion of the patient's symptoms or pathology. The investigator will identify the primary target vein and any additional qualifying target veins to be treated prior to the randomization for CEAP 2-5 subjects and prior to the index procedure for CEAP 6 subjects. The primary target vein will be treated first during the index procedure, and the remaining target veins will be treated in succession.

If more than one vein requires treatment in the target limb, the treating physician will indicate which vein is the primary target vein in the CRFs and track the veins accordingly throughout the study. In the case of bilateral disease with both limbs meeting study eligibility criteria, the investigator should designate the more severe limb (higher CEAP score or most symptomatic according to patient, per treating physician's discretion) target limb. Treatment of the contralateral limb must be staged at least 30 days prior to or at least 3 months post-index procedure.

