7.8	Interim Analyses.....	23
7.9	Evaluation of Objectives	23
7.10	Safety Evaluation.....	52
7.11	Health Outcomes Analyses	53
7.12	Changes to Planned Analysis.....	53
8.	Validation Requirements.....	54

9. References	54
10. Statistical Appendices.....	54

1. Version History

Version	Summary of Changes	Author(s)/Title
1.0	
 Not Applicable, New Document 	[name], Principal Statistician
2.0	
 Update to note that elimination of truncal reflux will be summarized without hypothesis testing for the VenaSeal vs. Surgical Stripping Study, due to halted enrollment in sections 4.1, 7.5 and 7.9. Updated study design consistent with CIP changes in sections 5.1, 5.2, 6.2 and 7.9.3 (halting of Venaseal vs. Surgical Stripping study enrollment and reducing follow-up to 12 months and reduction in sample size of the VLU study) Add note on handling of VenaSeal vs. Surgical Stripping study data collected beyond 12 months in section 7.1.1 Added the scoring algorithm for the VenousTSQe and VenousTSQs in section 7.9.1.1.4 Added test for superiority in non-inferiority is met in section 7.9.1.2.3 Document updated using new template. 	[name], Principal Statistician
3.0	
 Re-organized the document so that each study endpoint is enumerated and the corresponding hypothesis, endpoint definition, analysis methods and analysis population are provided Return-to-work endpoints, return-to-normal activities, anatomic closure endpoints all revised use a time-to-first-event analysis to allow for censoring and incorporation of unscheduled follow-up visits Reintervention and healthcare utilization endpoints are revised to use a rate-based calculation to allow for potential recurrent events and differences in follow-up time Updated scoring of the VenousTSQe and VenousTSQs based on the final recommendations 	[name], Distinguished Statistician

2. List of Abbreviations and Definitions of Terms

Abbreviation	Definition
AE	Adverse Event

Abbreviation	Definition
AVVQ	Aberdeen Varicose Vein Questionnaire
CEAP	Clinical, Etiological, Anatomical, and Pathophysiological Classification
CIP	Clinical Investigation Plan
CRF	Case Report Form
DUS	Duplex Ultrasound
DVT	Deep Vein Thrombosis
EGIT	Endovenous glue induced thrombosis
EHIT	Endovenous heat induced thrombosis
EQ-5D	EuroQoL 5 Dimensions Standardized Quality of Life Survey
EVLA	Endovenous Laser Ablation
ETA	Endovenous Thermal Ablation

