5.1 Study Design

The study design is a global, post-market, prospective, multi-center, randomized-controlled study of patients with symptomatic superficial venous disease, with a single-arm embedded ulcer group. The study is designed with two Randomized Studies (VenaSeal vs. Surgical Stripping Study and VenaSeal vs. ETA Study) for CEAP 2-5 subjects and one single arm active VLU Study for CEAP 6 subjects. Each study will be individually assessed and analyzed for the overall study objectives.

There will be approximately 500 subjects enrolled in the VenaSeal Spectrum Study. Approximately 375 subjects will be enrolled in CEAP clinical classifications 2-5 in the Randomized Studies (108 subjects in VenaSeal vs. Surgical Stripping Study and about 264 subjects in VenaSeal vs. ETA Study), and up to 125 CEAP 6 subjects with VLUs will be treated with the VenaSeal™ system.

Enrollment of the VenaSeal vs. Surgical Stripping Study was closed on 22-Feb-2022. All subjects participating in the VenaSeal vs ETA Study or in the VLU Study (CEAP 2-6) will be followed up to 60 months post-index procedure, all subjects participating in the VenaSeal vs. Surgical Stripping Study will be followed up to 12 months post-index procedure.

Enrollment will take place at up to 40 sites globally.

To avoid introduction of bias to the study results due to disproportionate enrollment, enrollment at any individual site shall not exceed 20% of any single study (approximately 50 subjects for the Randomized Studies and 25 subjects for the VLU Study, excluding screen failures) of the total sample size. It is expected that sites enroll a minimum of 10 subjects per individual study the site is participating in. Enrollment was halted early for the VenaSeal vs. Surgical Stripping study, so control of each site's contribution to the overall total was not possible.

Randomization will be stratified by study site and CEAP classification 2/3 vs. 4/5. There is no blinding in this study. The detailed procedure of randomization information is described in the Randomization and Blinding Plan separately.

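### Reintervention is reported per vein-year but tested per person-year, and the Poisson model makes no provision for events that cluster within subjects

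*SAP*

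**What the plan says.** For the summary, SAP 7.9.1.4 item 4 states that "the denominator is the number of vein-years of follow-up" and defines that quantity: "The vein-years is the amount of person-years times the number of target veins". The next sentence specifies the test as a Poisson model "using the number of reinterventions as the outcome and the person years of follow-up as an offset". The two-sided hypothesis says only that its parameters "are the rates of reintervention in the VenaSeal™ system arm and the ETA or surgical stripping arm, respectively", without stating the exposure.

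The SAP version history explains that version 3.0 moved this endpoint to a "rate-based calculation to allow for potential recurrent events and differences in follow-up time". Item 4 nevertheless names no scale parameter, robust variance, negative binomial model or subject effect. It also gives no expected rate and no confidence interval.

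The two exposures can differ because protocol 9.3 allows "Multiple refluxing superficial truncal veins (e.g., GSV, SSV, accessory saphenous veins) in the same target limb" to be treated. The same section has the investigator identify the primary target vein and "any additional qualifying target veins to be treated prior to the randomization for CEAP 2-5 subjects", so vein count is a baseline variable. Neither document says how many subjects are expected to have more than one target vein.

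**The concern.** There are two separate issues.

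**Exposure.** A report that follows the SAP would place per-vein-year rates beside a p-value from a per-person-year comparison. If the arms differ in mean vein count, the two can disagree, and a reader would not know which rate the null hypothesis concerns.

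**Variance.** A plain Poisson model sets the variance of the count equal to its mean. Once repeat events in one subject count, subjects who differ in underlying risk give a variance larger than the mean. The model's standard error is then too small and its p-value too optimistic. With up to 60 months of follow-up in the ETA study there is time for repeats to accumulate. Choosing the variance after seeing the counts would be a data-driven decision, so it belongs in the SAP now.

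**Working it through.** **No planned figure to reproduce.** Neither document gives an expected rate, power or interval for this endpoint.

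**Inputs from the documents.** "108 subjects in VenaSeal vs. Surgical Stripping Study and about 264 subjects in VenaSeal vs. ETA Study" (SAP 5.1); 1:1 allocation (protocol 10.4); follow-up to 60 months (ETA) or 12 months (stripping); p-values for the other secondary endpoints unadjusted (SAP 7.9.1.3).

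**Assumptions, because the documents give none.** 0.01, 0.03 or 0.06 reinterventions per vein-year; 0%, 15% or 30% of subjects with two veins; gamma frailty variance k = 0, 2, 5 or 10; 5% dropout per year; nominal two-sided 0.05.

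**Step 1: the two ratios.** With equal follow-up,

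per-person-year ratio = per-vein-year ratio × (mean veins, VenaSeal arm ÷ mean veins, control arm).

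For equal per-vein-year rates and 1.10 vs 1.20 veins per subject, the tested ratio is 1.00 × 1.10/1.20 = 0.917. With equal vein mix the ratios agree.

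**Step 2: size of the chance gap.** If a fraction p of subjects has two veins, the relative standard error of the gap is about √(p(1−p)) × √(2/n) ÷ (1+p), with n per arm. For p = 0.30 and n = 132: 0.458 × √(2/132) ÷ 1.30 = 0.043. The median absolute gap is 0.6745 × 0.043 = 2.9% and the 95th percentile 1.96 × 0.043 = 8.5%. For p = 0.15 they are 2.6% and 7.5%. Simulation, which adds dropout, gives about 3% and 8-10% at N = 264, and about 4-5% and 12-15% at N = 108.

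**Step 3: closed form for the variance.** Variance inflation φ = 1 + k × (mean count per subject); true type I error = 2(1 − Φ(1.96/√φ)). At 0.03 per vein-year, 1.3 veins and 5 years without dropout, the mean count is 0.03 × 1.3 × 5 = 0.195.
- k = 2: φ = 1.39, √φ = 1.18, type I error 9.6%.
- k = 5: φ = 1.975, √φ = 1.41, type I error 16.3%.

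**Step 4: simulation under the null.** 4,000 runs per setting, ETA study, 30% with two veins, person-year offset, Wald test. Cells show true SE ÷ Poisson SE, then type I error.

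| Rate per vein-year | k = 2 | k = 5 | k = 10 |
|---|---|---|---|
| 0.01 | 1.05; 0.050 | 1.12; 0.062 | 1.21; 0.096 |
| 0.03 | 1.18; 0.094 | 1.38; 0.160 | 1.63; 0.252 |
| 0.06 | 1.34; 0.144 | 1.70; 0.264 | 2.11; 0.390 |

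Without frailty, differing vein counts alone give an SE ratio of only 1.00-1.02.

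**Step 5: what each change does (rate 0.03, 30% with two veins).**
- Vein-year offset alone: 0.052 to 0.046 at k = 0; 0.160 either way at k = 5.
- Sandwich variance, person-year offset: 0.094 to 0.056 at k = 2; 0.160 to 0.059 at k = 5; 0.052 vs 0.053 at k = 0.

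The sandwich correction is not perfect: at rate 0.06 it leaves 0.068 (k = 5) and 0.074 (k = 10).

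**Step 6: stripping study (N = 108, 12 months).** At rates 0.03-0.06 the SE factor is 1.01-1.19 with frailty, and type I error is about 0.05 or below because events are few. Runs with no events in one arm were dropped.

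**Plausibility check.** Protocol 4.1 reports 60-month freedom from recanalization of 91.4% (VenaSeal) and 85.2% (RFA) in the extension of the earlier randomized trial. Treating the complements as 0.086 and 0.148 events per subject, with k = 1 to 3, φ runs from 1.086 to 1.444 and type I error from 6.0% to 10.3%. Recanalization is not reintervention, so this only indicates scale.

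**The case against.** The strongest reply is that little turns on this. Vein count is fixed before randomization, so a per-person-year comparison is a valid comparison of per-patient rates, and the gap between the two ratios is typically a few percent. Reintervention is one of many secondary endpoints with unadjusted p-values. Item 5 of the same section adds a Kaplan-Meier and log-rank analysis of time to first reintervention, which repeat events do not disturb. All of that stands and limits the importance of the point. It does not reconcile two adjacent sentences that use different exposures, or supply the missing variance provision.

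A reader might infer three stronger things that the documents do not support:
- **That the standard error is too small.** This requires clustering within subjects at a material event rate. Neither document gives either figure, and the version history speaks only of potential recurrence. If events are rare and seldom repeat, Poisson is adequate. No interval is planned for this endpoint, so the exposure to error is in the p-value.
- **That the uneven vein counts themselves distort the test.** They add almost no overdispersion, and changing the offset barely moves type I error.
- **That a principal durability claim is at risk.** The multiplicity-controlled claims of the ETA study are the two 30-day satisfaction scores, truncal disease elimination, 6-month closure and return to work.

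**Conclusion.** The point holds as a clarification that should be made, not as a fault that invalidates the comparison. The exposure mismatch is certain from the text. Its numerical effect is small in the ETA study and somewhat larger in the stripping study, on the assumption that 15-30% of subjects have two veins. The missing provision for overdispersion is also certain. Its consequence is conditional: in the ETA study, type I error ranges from about 5% (0.01 per vein-year, k = 2) to about 9-16% (0.03 per vein-year, k = 2-5), and higher under heavier clustering or higher rates. These figures rest on assumed rates and frailty variances. The 12-month stripping study gives little cause for concern on variance.

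**What to change.** In SAP 7.9.1.4 item 4:
- Use one exposure for both the rate and the test: either log(vein-years) as the offset, or a rate reported per person-year. Name that rate in the hypothesis. A vein-year offset assumes risk proportional to vein count; a person-year rate answers a per-patient question. Either is acceptable if used throughout.
- If vein-years are kept, state that the primary target vein is counted. Protocol Appendix B defines target veins as those beyond the primary one, whereas this endpoint includes it.
- Fit one record per subject with a robust (sandwich) variance.
- Report the rate ratio with a 95% confidence interval.

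The cost is a few lines of SAP text and a model option. Intervals will be slightly wider if events cluster, and essentially unchanged if they do not. A negative binomial model is an alternative, but its dispersion parameter is poorly estimated when events are few, so the sandwich variance is the steadier choice.
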